patients will be enrolled. As this is a competitive enrollment study, MUSC will enroll up to 75 volunteers. Eligibility will be determined by each site PI. The PI or Co-I will explain the study to qualified subjects prior to obtaining consent. The subject will also be given an opportunity to review and sign documentation of HIPAA compliance and authorization.

Inclusion criteria:

Patients to be included for participation in this study are:

- 1) Patients with a solid lung lesion 1.5-5cm identified on chest CT (obtained within previous 3 months) with the intention to undergo bronchoscopic evaluation. If the lesion is partially solid (i.e. there is a ground glass component) then the solid portion must make up >75% of the lesion and measure at 1.5-5cm. The decision to pursue biopsy will be made by the treating physician and agreed upon by the patient. This will include patients determined to have an intermediate risk of malignancy (5-65%) and those non-surgical candidate with higher risk lesions in need of diagnosis for alternative treatment. OR
- 2) Patients with a solid lung lesion 1.5-5cm identified on chest CT (obtained within previous 3 months) that are surgical candidates with a high probability of cancer (>65%) will be referred for surgical evaluation. If the lesion is partially solid (i.e. there is a ground glass component) then the solid portion must make up >75% of the lesion and measure at 1.5-5cm. If the patient refuses surgery or if the surgeon requests a definitive diagnosis prior to surgery the patient will have the option to be included in this study. All sites will use the same online calculator to document probability of malignancy.
- 3) Patients whose targeted lung lesion is visualized with fluoroscopy
- 4) Are at least 22 years old,
- 5) Lack Bleeding disorders, and
- 6) Are able to provide informed consent.

Race and gender inclusion will reflect the population characteristics found in the respective regions.

Exclusion criteria:

Patients to be excluded from participation in this study are:

- 1) Patients with a pure ground-glass opacity identified on chest CT
- 2) Patients with endobronchial involvement seen on chest CT.
- 3) Patients who refuse to participate,
- 4) Are less than 22 years of age,
- 5) Lack fitness to undergo flexible bronchoscopy as determined by the bronchoscopist prior to procedure, and
- 6) Are unable to provide informed consent
- 7) Pregnant

INFORMED CONSENT:

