If a diagnosis is not obtained after the procedure, further recommendations regarding treatment will be made by the treating physician. (i.e. follow-up CT chest, CT guided transthoracic needle aspiration, or surgery). In the standard FB arm, the bronchoscopist will have the option of using peripheral ultrasound with or without the ultrathin scope to attempt to identify the lesion. Specimens obtained must be kept separate and identified as having performed using R-EBUS (e.g. labelled "radial brush", "radial biopsy") and reflected in the case report form. If ROSE is non-diagnostic and/or indicates chronic inflammation, crossover to the Ultrathin bronchoscope with R-EBUS will take place. In those patients that cross over to the Ultrathin bronchoscope with R-EBUS the same protocol for those randomized to the ultrathin/R-EBUS arm will be followed (see #3).

RISKS OF PROCEDURES:

The greatest risks from bronchoscopy are related to moderate or deep sedation and the very act of passing a bronchoscope into the airway. To mitigate risks of bronchoscopy all patients will be monitored by a nurse and a respiratory therapist during the procedure. In addition, oxygen saturation (using pulse oximetry) respiratory rate, blood pressure, ECG, and heart rate will be continuously monitored. Patients will not be released until they are fully awake and medically stable.

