Confirmation of the diagnosis by surgery or repeat imaging will be recorded for those patients who have non-diagnostic results (including chronic inflammation) from the study procedures. If the patient is referred for surgery, the surgical pathology will be considered the final diagnosis. If the patient has follow-up imaging that shows resolution of the lesion, the lesion will be determined to be of benign etiology. To verify final diagnosis, a copy of the final pathology report from bronchoscopy and any pathology reports from subsequent surgical resection, will be de-identified and provided by the site to the coordinating center.

(5) Complications:

Adverse event rates will be documented. Pneumothorax will be documented by post-biopsy CXR or chest ultrasonography, and the number requiring intervention, such as chest tube placement, will be recorded. Significant hemoptysis will be defined as bleeding noted at the time of procedure that requires a change in the level of care (e.g. outpatient to inpatient or inpatient to ICU) or a blood transfusion. Other adverse events that are common to bronchoscopy described above in "Risks" section will be monitored and reported by the patient or nursing staff.

DATA SAFETY MONITORING PLAN

All subjects enrolled in the trial will undergo routine standard of care bronchoscopy that is indicated a medically necessary by their physicians. Prior to the bronchoscopic procedure, PIs will explain the risks associated with bronchoscopy, and verify that the research only risks have been explained, and that the subject has signed an informed consent form. There are no anticipated risks, outside of the risk for the standard of care procedures for this clinical trial. All subjects are required to read, understand, and sign the informed consent form associated with the research study. Each subject will be informed of post procedure symptoms of which to be aware that may represent adverse reactions to the bronchoscopy. Symptoms that the patient will be informed to look out for include:

- Pain or difficulty with swallowing
- Difficulty breathing
- Vomiting
- Dizziness
- Abdominal or chest pain
- Continuous bright red blood in your sputum
- Fever above 100.0 degrees Fahrenheit

If the subject notes any of these symptoms, he/she is instructed to contact his/her physician, who will determine the course of action. All events are to be reported within 48 hours of occurrence to the coordinating site (MUSC). All adverse events (AEs) will

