Each site investigator will review the results, and the results will become part of the subject's medical record and research record. Any clinical follow-up or repeat procedures will be dictated by the patient's physician based on clinically relevant data and will not be influenced by enrollment into this study. To protect subject

confidentiality, MUSC will receive all sites' data as de-identified through use of the 6 digit patient codes. All information and data related to this study will be stored in a secured, locked cabinet in MUSC Clinical Sciences Building Room 809. The privacy of subjects will be protected using a 6 digit computer generated random code. The key to the code will be kept in a password protected folder on the MUSC DB2 (\DA) server; access to this folder is restricted to study personnel alone.

Electronic Data will be entered and stored in the secure REDCap database created for this study. REDCap is a web-based application designed exclusively to support data capture for research studies. It provides an intuitive interface for data entry, audit trails for tracking data manipulation and export procedures, procedures for importing data from external sources, advanced features such as branching logic and calculated fields, and automated export procedures for seamless data downloads to common statistical packages such as SPSS, SAS, Stata, and R. It was developed at Vanderbilt University (see <http://redcap.vanderbilt.edu/consortium/index.php>) and is ideal for remote data entry, as will be the case for this multi-center trial.

III. STATISTICAL ANALYSIS:

Statistical comparisons will be made using chi-square analysis where applicable. Sensitivity, specificity, positive and negative predictive value and accuracy of all procedures will be calculated. A logistic regression analysis of factors influencing tissue quantity will be undertaken.

Coordinating Center: MUSC will be the designated coordinating center for this trial. MUSC will be responsible for development of the database, housing the data, working with the sites on IRB issues, patient enrollment, completion of on-line data collection instrument and validation of the data. MUSC will also be responsible for payment to the sites when a patient's case report form is complete and query-free. Statistical support and interim analysis will be performed at MUSC by an in house statistician ([name]). Interim results will be shared with all participating sites during teleconference meetings.

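### The confirmation rules after a non-diagnostic bronchoscopy leave out needle aspiration and other non-surgical biopsy, so missed cancers may go unverified and each arm's sensitivity may be overstated

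*Combined protocol and SAP*

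**What the plan says.** Data Collection (4), Confirmation of Diagnosis, sets what is recorded after a non-diagnostic study procedure: "Confirmation of the diagnosis by surgery or repeat imaging will be recorded for those patients who have non-diagnostic results". It gives two rules for the final diagnosis. For surgery: "If the patient is referred for surgery, the surgical pathology will be considered the final diagnosis". For imaging: "If the patient has follow-up imaging that shows resolution of the lesion, the lesion will be determined to be of benign etiology". For verification, sites send the final bronchoscopy pathology report and "any pathology reports from subsequent surgical resection, will be de-identified and provided by the site to the coordinating center".

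Three other places bear on this.

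- Bronchoscopy Procedures (6) lists the possible next steps after a non-diagnostic procedure: "follow-up CT chest, CT guided transthoracic needle aspiration, or surgery".
- Inclusion criterion 1 admits patients described as "non-surgical candidate with higher risk lesions in need of diagnosis for alternative treatment".
- Data Collection (3) follows non-diagnostic patients for up to one year, until a definitive diagnosis or a decrease of the lesion on CT. It names surgical pathology as an example of such a diagnosis, not as the sole source.

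Section III, Statistical Analysis, states: "Sensitivity, specificity, positive and negative predictive value and accuracy of all procedures will be calculated". It defines no reference standard, no denominator and no handling of patients whose status stays unconfirmed. The primary outcome, diagnostic yield, is taken from the bronchoscopy result (Data Collection (3)).

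**The concern.** Sensitivity and NPV need the true status of patients whose bronchoscopy gave no diagnosis. The protocol foresees that some of them will go to needle aspiration. It also enrols a group with higher-risk lesions in whom surgical confirmation is unlikely. For these patients section (4) gives no rule that turns a needle result into a final diagnosis, and it does not request the report. Section (3) is worded more openly, so the two sections do not agree, and with up to eight collaborating centers sites could read them differently.

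A cancer missed at bronchoscopy and later proven by needle is a false negative. If its proof never reaches the coordinating center, the analyst cannot recover it at the end. At stake are the accuracy measures in section III, not the primary comparison.

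**Working it through.** **Step 1. Routes against rules.**

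| Route after a non-diagnostic procedure | Listed in Procedures (6) | Final-diagnosis rule in Data Collection (4) | Report requested in (4) |
|---|---|---|---|
| Surgery | yes | yes | yes, resection pathology |
| Follow-up CT | yes | only if the lesion resolves | none |
| CT-guided needle aspiration | yes | none | no |
| Repeat bronchoscopy, other biopsy | not named | none | not named |

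**Step 2. The plan's own figure.** Inputs from Bronchoscopy Procedures: yields of 50% and 70%, two-sided alpha 0.05, power 85%. With pooled variance under the null and no continuity correction:

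n = [1.960 × √(2 × 0.6 × 0.4) + 1.036 × √(0.5 × 0.5 + 0.7 × 0.3)]² / 0.2² = (1.358 + 0.703)² / 0.04 ≈ 106.2, so 107 per arm.

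Power at 107 per arm is 85.3%. The stated figure is reproduced. It uses yield alone, so it does not depend on how later diagnoses are confirmed.

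**Step 3. Sensitivity if unverified misses are dropped.** The documents give no prevalence of cancer, no true sensitivity and no share of misses proven only by needle. I take sensitivity to mean sensitivity for cancer and borrow the planning yields as true sensitivity s (50% standard, 70% R-EBUS). Let f be the share of missed cancers that is lost. Then

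apparent sensitivity = s / [s + (1 − s)(1 − f)].

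Prevalence cancels. With f = 50%: 0.5 / (0.5 + 0.25) = 66.7%, and 0.7 / (0.7 + 0.15) = 82.4%.

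| f, equal in both arms | Standard | R-EBUS | Difference (points) |
|---|---|---|---|
| 0% | 50.0% | 70.0% | 20.0 |
| 25% | 57.1% | 75.7% | 18.5 |
| 50% | 66.7% | 82.4% | 15.7 |
| 75% | 80.0% | 90.3% | 10.3 |

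Each arm's sensitivity rises for any f above zero.

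**Step 4. Unequal loss.** With f = 25% standard and 50% R-EBUS, the values are 57.1% and 82.4%, a difference of 25.2 points. With 50% and 25% they are 66.7% and 75.7%, a difference of 9.0 points.

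**Step 5. Crossover.** Under Procedures (6), standard-arm patients with a non-diagnostic on-site reading cross over to ultrathin R-EBUS, with the specimens kept separate. A cancer found that way is verified in the same session and stays in the standard arm's denominator. Suppose that every standard-arm miss crosses over and that the two procedures together find as many cancers as R-EBUS alone. Per 100 cancers in each arm, standard bronchoscopy finds 50, crossover verifies 20 more, and 30 stay unverified, the same number as in the R-EBUS arm. Dropping half of the 30 gives 50/85 = 58.8% against 70/85 = 82.4%, a difference of 23.5 points. The contrast now widens.

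Other inputs show the same pattern. Assume 75 cancers per arm and true sensitivities of 60% and 80% (45/75 and 60/75), with one third of the unverified misses lost. Without crossover: 45/65 against 60/70, or 69.2% against 85.7%, 16.5 points. With crossover: 45/70 against 60/70, or 64.3% against 85.7%, 21.4 points.

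**Step 6. NPV.** NPV = TN / (TN + FN). If a share g of true negatives (for example, needle-proven benign lesions) is lost along with a share f of false negatives, it becomes TN(1 − g) / [TN(1 − g) + FN(1 − f)]. It rises if f exceeds g and falls if g exceeds f. The documents give neither share.

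**The case against.** The best reply is that nothing is excluded. Section (3) leaves the source of a definitive diagnosis open, section (4) never says that surgery and imaging are the sole sources, and the case report form, which is not among the documents, may already have a field for later procedures. This stands against the reading that a final diagnosis can come only from surgery or imaging. It does not close the gap: section (4) is where recording and verification are specified, and there needle pathology has neither a rule nor a requested report.

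Four further inferences are tempting but not supported.

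- **That needle-proven cancers leave the denominator.** No denominator is written. Such patients could be counted as misses, dropped or left unresolved. The calculation shows what happens if they are dropped.
- **That the contrast between arms shrinks.** This needs a similar loss in both arms and no verification through crossover. Steps 4 and 5 show that it can also widen.
- **That NPV is overstated.** Step 6 shows that the direction is open.
- **That a needle-proven cancer, once treated and resolved, is relabelled benign.** Under section (3) that patient reaches a definitive diagnosis before treatment. The imaging rule also requires resolution, not mere shrinkage. The route is weak for these patients, although the rule has no safeguard for a lesion treated as cancer in between.

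It is also fair that the stakes are limited. Sensitivity and NPV are not among the listed primary or secondary outcomes, and a reduced need for needle aspiration appears in the rationale, not as an aim.

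**Conclusion.** The concern holds as a gap and an inconsistency in the reference standard. Section (4), followed as written, would leave unverified some missed cancers that the protocol itself expects to be diagnosed by needle, and section (3) points the other way. If those patients are dropped, sensitivity is biased upward in each arm. Under the assumed 50% and 70%, the apparent values run from 57% to 80% and from 76% to 90% as the share of misses lost goes from 25% to 75%. The size rests wholly on assumed inputs; the upward direction within an arm rests only on the patients being dropped. The effect on the between-arm difference (9.0 to 25.2 points in the unequal-loss examples, against a true 20) and on NPV cannot be signed from the documents. The primary yield, the 107 per arm and the 85% power are untouched. This should be corrected because the missing information cannot be reconstructed at analysis, but it does not threaten the main result.

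**What to change.** Revise Data Collection (4) and bring (3) into line with it.

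1. Accept as final diagnosis any later tissue diagnosis of the target lesion within the one-year follow-up: needle aspiration, repeat bronchoscopy, other biopsy or surgery.
2. Have sites send that de-identified report, as they already do for resections, and add a case report form field for the type and date of each later procedure, unless one exists.
3. Count resolution on imaging as benign only if no cancer treatment was given in between.
4. In section III, define the denominators of sensitivity and NPV and state how patients unresolved at one year enter them, for example by showing both extremes (all counted as cancer, all counted as benign).

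The cost is a paragraph of protocol text, one form field and a few more reports from patients already in follow-up. No procedure is added and the sample size stays the same. The downside is that reported sensitivity will probably look somewhat less favourable.

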The radiographic information collected will include location of the lesion, size of the lesion, distance from a visible bronchus, and PET characteristics. For R-EBUS procedures, a jpeg ultrasound image of the lesion will be recorded, anonymized, and uploaded to the REDCap study data collection instrument. The location of the lesion (side, lobe and segment, i.e. right upper lobe anterior segment, etc.) will be determined and recorded. The size of the lesion in longest axis diameter will be measured and recorded. The distance from the trachea as calculated as the number of generations from the main carina (first generation) to the lesion will be recorded. All central and peripheral lesions considered intermediate risk will be included. If the patient has undergone a PET, the metabolic activity (measured SUV) will be recorded.

(2) Procedural Characteristics:

The procedural information will include the number of biopsy passes, types of biopsy performed (TBBx, , brush, BAL), and R-EBUS description of site of biopsy of the lesion (within vs. adjacent to) will be recorded. The time length of procedure, type and amount of sedation administered will also be recorded.

(3) Diagnostic Yield and Crossover Procedures:

Primary outcome of diagnostic yield will be determined from the results of the bronchoscopy. A biopsy that results in a specific diagnosis, either malignant or benign, will be assumed to be a true positive. Plan for further diagnostic management for patients who have a non-diagnostic biopsy (and/or biopsy indicating chronic inflammation) will be determined by the attending physician. Those patients will be followed for up to one year until a definitive diagnosis has been made (such as from

surgical pathology), or the lesion has decreased on repeat CT imaging. Under standard procedure randomization, if ROSE indicates chronic inflammation, crossover to R-EBUS will take place.

(4) Confirmation of Diagnosis:

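### After a non-diagnostic bronchoscopy, a lesion that resolves on imaging is ruled benign even if it was treated as cancer without tissue, which can overstate the planned accuracy measures

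*Combined protocol and SAP*

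**What the plan says.** The final diagnosis of a lesion left undiagnosed by the study procedures is governed by DATA COLLECTION, (4) Confirmation of Diagnosis. It names two routes, surgery and repeat imaging. For surgery: "If the patient is referred for surgery, the surgical pathology will be considered the final diagnosis". For imaging: "If the patient has follow-up imaging that shows resolution of the lesion, the lesion will be determined to be of benign etiology". The imaging sentence says nothing about treatment received before the scan.

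Four other places bear on how that sentence works.

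- Inclusion criterion 1 admits intermediate-risk patients and also "those non-surgical candidate with higher risk lesions in need of diagnosis for alternative treatment".
- BRONCHOSCOPY PROCEDURES, (6), on non-diagnostic procedures, says that "further recommendations regarding treatment will be made by the treating physician" and gives follow-up CT, CT-guided needle aspiration and surgery as examples.
- DATA COLLECTION, (3), on follow-up: "Those patients will be followed for up to one year until a definitive diagnosis has been made", or until the lesion has become smaller on CT.
- III. STATISTICAL ANALYSIS: "Sensitivity, specificity, positive and negative predictive value and accuracy of all procedures will be calculated".

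The items listed under DATA COLLECTION, (1) to (5), cover imaging, procedure, yield and crossover, confirmation and complications. Cancer-directed treatment after the procedure is not among them. The pathology to be sent to the coordinating center is that from bronchoscopy and from later resection.

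**The concern.** Disappearance of an untreated lesion is reasonable evidence that it was benign. Disappearance after cancer-directed treatment is not, because the treatment may have caused it. The rule treats the two alike.

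The patients most exposed are those for whom surgical pathology is least likely to be available: higher-risk patients who are not candidates for surgery. For them imaging is the only other route named for a final diagnosis. If the bronchoscopy misses a cancer, the lesion is then treated without tissue, and it resolves within follow-up, the stated rule records a benign lesion. From the listed data an analyst could not tell this patient from one whose lesion cleared on its own.

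At stake are the accuracy measures. In a conventional table with malignancy as the target condition, such a patient moves from false negative to true negative. Sensitivity, negative predictive value (NPV) and accuracy all rise, and the rise reflects local treatment practice as well as the number of cancers missed.

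**Working it through.** **The plan's own figure.** The sample size assumes yields of 50% and 70%, two-sided alpha 0.05 and 85% power. With the pooled-variance formula and no continuity correction:

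n = [1.960·√(2·0.6·0.4) + 1.036·√(0.5·0.5 + 0.7·0.3)]² / 0.20² = (1.358 + 0.703)² / 0.04 ≈ 106.2, so 107 per arm. Power at 107 per arm is 85.3%.

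This agrees with the plan. It does not depend on the imaging rule, because DATA COLLECTION, (3) takes the primary yield from the bronchoscopy result.

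**Inputs for the illustration.** From the documents: 107 patients per arm. Assumed, because the documents do not give them:

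- prevalence of malignancy P = 60–80%;
- true sensitivity Se = 50% or 70% (borrowed from the planned yields, which are not themselves sensitivities);
- no false-positive cancer diagnoses;
- f = 5–20%, the share of missed cancers that are treated without tissue and also resolve within follow-up.

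**Formulas.** Cancers D = 107·P, benign B = 107 − D, missed cancers FN = D·(1 − Se). The rule moves f·FN patients to benign. Then:

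- apparent sensitivity = Se / [1 − f(1 − Se)], which does not depend on prevalence;
- true NPV = B / (B + FN), apparent NPV = (B + f·FN) / (B + FN);
- rise in accuracy = f·FN / 107.

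**Results at P = 70%** (D = 74.9, B = 32.1):

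| True Se | FN | f | Patients moved | Sensitivity | NPV | Accuracy |
|---|---|---|---|---|---|---|
| 50% | 37.4 | 0 | 0 | 50.0% | 46.2% | 65.0% |
| 50% | 37.4 | 5% | 1.9 | 51.3% | 48.8% | 66.8% |
| 50% | 37.4 | 10% | 3.7 | 52.6% | 51.5% | 68.5% |
| 50% | 37.4 | 20% | 7.5 | 55.6% | 56.9% | 72.0% |
| 70% | 22.5 | 0 | 0 | 70.0% | 58.8% | 79.0% |
| 70% | 22.5 | 5% | 1.1 | 71.1% | 60.9% | 80.1% |
| 70% | 22.5 | 10% | 2.2 | 72.2% | 62.9% | 81.1% |
| 70% | 22.5 | 20% | 4.5 | 74.5% | 67.1% | 83.2% |

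**Range over P = 60–80% and f = 5–20%.** Sensitivity rises by 1.1 points (70% to 71.1%) up to 5.6 points (50% to 55.6%). NPV rises by about 1.5 points (69.0% to 70.5%, at Se 70%, P 60%, f 5%) up to 13.3 points (33.3% to 46.7%, at Se 50%, P 80%, f 20%). A prevalence below 60% would make the NPV effect smaller.

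**Between arms.** With the same f in both arms, more patients move in the arm that misses more cancers (3.7 against 2.2 at f = 10%), so the NPV difference narrows from 58.8 − 46.2 = 12.6 points to 62.9 − 51.5 = 11.4. The share f need not be equal, however: crossover from the standard arm gives those patients a second attempt at tissue. The direction of any between-arm effect is therefore not fixed by the documents.

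**The case against.** The strongest case against is that the sequence is hypothetical. No section describes treating a lesion as cancer without tissue. Inclusion criterion 1 says that the non-surgical patients need a diagnosis so that they can be treated; the examples given after a non-diagnostic result are two tissue routes and surveillance; and follow-up aims at a definitive diagnosis. An error also requires complete resolution within at most one year. All of this stands, and it is why no frequency can be stated. It does not remove the gap: treatment without tissue is not excluded, care is left to the physician, and the rule would give the wrong label when it happened.

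Several stronger readings are tempting and are not supported:

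- *That every resolving lesion is affected.* The rule applies only after non-diagnostic study procedures, and surgical pathology is final for patients referred for surgery.
- *That all missed cancers in treated non-surgical patients become true negatives.* Only those that resolve could. The plan also does not define a true negative, and it counts a specific benign biopsy as a true positive, so the shift described here presupposes a malignancy-based table.
- *That about 86 patients are exposed* (107·0.50 + 107·0.30 = 85.6). This ignores crossover from the standard arm. If all 53.5 standard-arm failures crossed over with an assumed yield of 40–70%, about 48 to 64 would remain (32.1 + 53.5·0.30 to 32.1 + 53.5·0.60). Only the missed cancers among them matter.
- *That the error could never be traced.* The case report form is not in the documents, and medical records exist. What can be said is that no listed item would reveal it.
- *That treated lesions should simply be called malignant.* Inclusion covers risks from 5% upward, so a benign lesion treated without tissue would then become a false negative.

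It is also fair to say that the accuracy measures are not among the named secondary outcomes. They are nevertheless planned, for all procedures.

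**Conclusion.** The concern holds in a limited form. For patients with non-diagnostic study procedures and no surgical pathology, the imaging rule would label as benign a missed cancer that was treated without tissue and resolved within follow-up, and the listed data would not show it. Under a malignancy-based table this overstates sensitivity, NPV and accuracy.

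The true size is unknown. Under the assumptions shown, sensitivity rises by about 1–6 points and NPV by about 1.5–13 points; these figures illustrate and do not estimate. A reader might infer that the primary comparison is compromised. It is not: the yield is read from the bronchoscopy result, and 107 per arm stands.

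**What to change.** Amend the imaging sentence in DATA COLLECTION, (4) so that resolution counts as benign only if the target lesion received no cancer-directed treatment between the bronchoscopy and that imaging. Class lesions treated without tissue as indeterminate, and report the accuracy measures twice more, once counting them as malignant and once as benign. Record cancer-directed treatment of the target lesion (yes/no, date) on the case report form.

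Two adjacent points could be settled in the same edit. State how the cells of the accuracy table are defined, since only the true positive is. Also state the final class of a lesion that shrinks without resolving: (3) ends follow-up at any decrease, while (4) speaks only of resolution.

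The cost is one sentence, one form field and a short sensitivity analysis. A few patients will have an indeterminate reference diagnosis, and reported sensitivity and NPV may be slightly lower or less precise. The change concerns classification and data capture only; it does not touch patient care.
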